4.1.2 Exclusion Criteria

Patients who meet any of the following criteria will be excluded from study entry:

- Grade 3b follicular lymphoma
- History of transformation of indolent disease to DLBCL
- Known CD20-negative status at relapse or progression
- CNS lymphoma or leptomeningeal infiltration
- Prior allogeneic SCT
- Completion of autologous SCT within 100 days prior to Day 1 of Cycle 1
- History of resistance to lenalidomide or response duration of < 1 year (for patients who had a response to a prior lenalidomide-containing regimen)
- Prior standard or investigational anti-cancer therapy as specified below:
 - Lenalidomide, fludarabine, or alemtuzumab within 12 months prior to Day 1 of Cycle 1
 - Radioimmunoconjugate within 12 weeks prior to Day 1 of Cycle 1
 - Monoclonal antibody or antibody-drug conjugate within 4 weeks prior to Day 1 of Cycle 1
 - Radiotherapy, chemotherapy, hormonal therapy, or targeted small-molecule therapy within 2 weeks prior to Day 1 of Cycle 1
 - Anti-PD-1, anti-PD-L1, anti-CTLA4, anti-CD137/41-BB agonist, or anti-CD40 agonist antibodies
- Clinically significant toxicity (other than alopecia) from prior treatment that has not resolved to Grade ≤ 2 (per NCI CTCAE v4.0) prior to Day 1 of Cycle 1

- Treatment with systemic immunosuppressive medications, including, but not limited to, prednisone, azathioprine, methotrexate, thalidomide, and anti-tumor necrosis factor agents within 2 weeks prior to Day 1 of Cycle 1

Treatment with inhaled corticosteroids and mineralocorticoids is permitted.

If corticosteroid treatment is urgently required for lymphoma symptom control prior to the start of study treatment, 100 mg of prednisone or equivalent can be given for a maximum of 5 days, but all tumor assessments must be completed prior to initiation of corticosteroid treatment.

- History of solid organ transplantation
- History of severe allergic or anaphylactic reaction to humanized, chimeric or murine monoclonal antibodies
- Known sensitivity or allergy to murine products
- Known hypersensitivity to biopharmaceuticals produced in Chinese hamster ovary cells or any component of the atezolizumab, obinutuzumab, or lenalidomide formulation, including mannitol
- History of erythema multiforme, Grade ≥ 3 rash, or blistering following prior treatment with immunomodulatory derivatives such as thalidomide and lenalidomide
- Known history of idiopathic pulmonary fibrosis, organizing pneumonia (e.g., bronchiolitis obliterans), drug-induced pneumonitis or evidence of active pneumonitis on screening chest CT scan.

History of radiation pneumonitis in the radiation field (fibrosis) is allowed.

- Active bacterial, viral, fungal, or other infection, or any major episode of infection requiring treatment with IV antibiotics within 4 weeks of Day 1 of Cycle 1

Caution should be exercised when considering the use of obinutuzumab in patients with a history of recurring or chronic infections.

- Positive for hepatitis B surface antigen (HBsAg), total hepatitis B core antibody (HBcAb), or hepatitis C virus (HCV) antibody at screening
- Known history of HIV positive status

For patients with unknown HIV status, HIV testing will be performed at screening if required by local regulations.

- History of progressive multifocal leukoencephalopathy
- Vaccination with a live virus vaccine within 28 days prior to Day 1 of Cycle 1 or anticipation that such a live, attenuated vaccine will be required during the study
- History of other malignancy that could affect compliance with the protocol or interpretation of results, with the exception of the following:

Any of the following malignancies, previously curatively treated: carcinoma in situ of the cervix, good-prognosis ductal carcinoma in situ of the breast, or basal or squamous cell skin cancer

Stage I melanoma, low-grade; early-stage localized prostate cancer; or any other previously treated malignancy that has been in remission without treatment for ≥ 5 years prior to enrollment

- History of autoimmune disease, including, but not limited to, myasthenia gravis, myositis, autoimmune hepatitis, systemic lupus erythematosus, rheumatoid arthritis, inflammatory bowel disease, vascular thrombosis associated with antiphospholipid syndrome, Wegener's granulomatosis, Sjögren's syndrome, Guillain-Barré syndrome, multiple sclerosis, vasculitis, or glomerulonephritis (see [Appendix 8](#) for a comprehensive list of autoimmune diseases)

Patients with a history of autoimmune-related hypothyroidism on a stable dose of thyroid-replacement hormone may be eligible for this study.

Patients with controlled Type 1 diabetes mellitus on a stable insulin regimen may be eligible for this study.

- Contraindication to treatment for TE prophylaxis (see Section [4.3.2.6](#))
- Grade ≥ 2 neuropathy
- Evidence of any significant, uncontrolled concomitant disease that could affect compliance with the protocol or interpretation of results, including significant cardiovascular disease (such as New York Heart Association Class III or IV cardiac disease, myocardial infarction within the previous 6 months, unstable arrhythmia, or unstable angina) or significant pulmonary disease (such as obstructive pulmonary disease or history of bronchospasm)
- Major surgical procedure other than for diagnosis within 28 days prior to Day 1 of Cycle 1 Day 1 or anticipation of a major surgical procedure during the course of the study
- Inadequate hematologic function (unless due to underlying lymphoma), defined as follows:
 - Hemoglobin < 9 g/dL
 - ANC $< 1.5 \times 10^9/L$
 - Platelet count $< 75 \times 10^9/L$
- Any of the following abnormal laboratory values (unless due to underlying lymphoma):
 - Calculated creatinine clearance < 60 mL/min (using the Cockcroft-Gault formula; see [Appendix 9](#))
 - AST or ALT > 2.5 times the upper limit of normal (ULN)
 - Serum total bilirubin $> 1.5 \times ULN$ (or $> 3 \times ULN$ for patients with Gilbert syndrome)
 - INR or PT $> 1.5 \times ULN$ in the absence of therapeutic anticoagulation
 - PTT or aPTT $> 1.5 \times ULN$ in the absence of a lupus anticoagulant

- Pregnant or lactating or intending to become pregnant during the study
 Women of childbearing potential must have two negative serum pregnancy test results (minimum sensitivity, 25 mIU/mL) prior to initiating therapy: at 10–14 days prior to Day 1 of Cycle 1 and within 24 hours prior to Day 1 of Cycle 1.
- Life expectancy <3 months
- Unable to comply with the study protocol, in the investigator's judgment

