3.1.2 Dose-Escalation Phase

The purpose of the dose-escalation phase is to identify the RP2D for lenalidomide when combined with fixed doses of obinutuzumab and atezolizumab as induction treatment (see Section 3.3.1).

Approximately 6–12 patients will be enrolled in the dose-escalation phase. Dosing groups of 3–6 patients each will be treated in accordance with the treatment regimens and the dose-escalation rules described in Section 3.1.2.2.

Patients will be closely monitored for adverse events during a DLT assessment window, defined as Cycle 2. Adverse events meeting the criteria for DLT, as defined below (see Section 3.1.2.1), will be reported to the Sponsor within 24 hours (see Section 5.4.2).

Patients who discontinue from the study prior to completing the DLT assessment window for reasons other than a DLT will be considered non-evaluable for dose-escalation decisions and for RP2D assessments and will be replaced by an additional patient at that same dose level. Patients who miss one or more doses of atezolizumab or obinutuzumab or five consecutive daily doses of lenalidomide during the DLT assessment window for reasons other than a DLT will also be replaced.

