3.1.2.1 Definition of Dose-Limiting Toxicity

In this study, a DLT is defined as any one of the following events occurring during Cycle 2 of treatment and assessed by the investigator as related to study treatment:

- Adverse event of any grade that leads to a delay of more than 14 days at the start of the next treatment cycle
- Hematologic adverse event that meets any of the following criteria:
 - Grade 3 or 4 neutropenia in the presence of sustained fever of $> 38^{\circ}\text{C}$ (lasting > 5 days) or a documented infection
 - Grade 4 neutropenia lasting > 7 days
 - Grade 3 or 4 thrombocytopenia that results in significant bleeding per investigator judgment
 - Grade 4 thrombocytopenia lasting > 7 days
- Grade 3 or 4 non-hematologic adverse event, with the following exceptions:
 - Grade 3 or 4 IRRs
 - Note that IRRs may occur even after a small amount of drug has been administered (i.e., IRRs are not dose dependent).
 - Grade 3 diarrhea that responds to therapy within 72 hours
 - Grade 3 nausea or vomiting that occurs in the absence of premedication and responds to adequate therapy within 72 hours

Other toxicities occurring during Cycle 2 that are considered to be clinically relevant and related to study treatment, as determined by the investigator and the Medical Monitor, may also be considered DLTs.

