
G-CSF = granulocyte colony-stimulating factor; LMWH = low-molecular-weight heparin.

^a Dose modifications apply only to events that are considered to be related to lenalidomide.

^b If cytopenia is thought to be caused mainly by non-Hodgkin's lymphoma infiltration of the bone marrow, the investigator may decide not to reduce the dose of lenalidomide.

^c For Grade 3 neutropenia, only if sustained (≥ 7 days) Grade 3 or \geq Grade 3 associated with fever (temperature $\geq 38.5^\circ\text{C}$).

Non-Hematologic Toxicities during Induction Treatment

[Table 11](#) provides guidelines for management of non-hematologic toxicities that occur during induction treatment.

Toxicities associated or possibly associated with atezolizumab treatment should be managed according to standard medical practice. Additional tests, such as autoimmune serology or biopsies, should be used to evaluate for a possible immunogenic etiology. For detailed information regarding management of adverse events associated with atezolizumab, please refer to the [Appendix 10](#).

Table 11 Guidelines for Management of Non-Hematologic Toxicities

Event	Action to Be Taken
General guidance for treatment delays and discontinuation	
 • If toxicity occurs before Cycle 1 Day 8 or Cycle 1 Day 15, these doses of obinutuzumab will not be skipped but given after resolution of toxicity. • When a treatment cycle is delayed because of a toxicity resulting from any component of the regimen, all study treatment should generally be held and resumed together to remain synchronized. • If it is anticipated that atezolizumab will be delayed by >21 days, obinutuzumab and lenalidomide should be given without atezolizumab if there is no contraindication. • If one drug is discontinued, treatment with the other two drugs may be continued for patients experiencing clinical benefit as determined by the investigator after discussion with the Medical Monitor. • Permanently discontinue study treatment if any of the following events occur: 
 – Grade ≥ 3 non-immune-mediated adverse event that is considered to be related to study treatment and does not resolve to Grade ≤ 2 within 21 days – Non-immune-mediated adverse event that is considered to be treatment related and requires study treatment to be withheld for >21 days – Immune-mediated adverse event that requires atezolizumab to be withheld for >42 days, unless approved by the Medical Monitor

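### A patient who enters dose escalation already at Grade 4 cytopenia from lymphoma counts as DLT-evaluable, although the two duration-based hematologic DLT criteria say nothing about dose for that patient

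*Combined protocol and SAP*

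**What the plan says.** **Entry.** Section 4.1.2, and the synopsis likewise, excludes patients with "Inadequate hematologic function (unless due to underlying lymphoma), defined as follows" and then lists limits for hemoglobin, ANC and platelets. Where lymphoma is the cause, no lower limit replaces them. Nothing confines the waiver to the expansion phase.

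**DLT definition.** Section 3.1.2.1 requires an event "occurring during Cycle 2 of treatment and assessed by the investigator as related to study treatment". Two hematologic criteria depend on grade and duration alone: "Grade 4 neutropenia lasting > 7 days" and "Grade 4 thrombocytopenia lasting > 7 days". The others need a clinical component, for example "Grade 3 or 4 thrombocytopenia that results in significant bleeding per investigator judgment"; the corresponding neutropenia criterion needs sustained fever or a documented infection. None refers to the baseline value, change from baseline or marrow involvement.

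**Evaluability.** Section 3.1.2 treats as non-evaluable, and replaces, patients who leave before the end of the window for a reason other than a DLT. It also replaces "Patients who miss one or more doses of atezolizumab or obinutuzumab or five consecutive daily doses of lenalidomide during the DLT assessment window" where the reason is not a DLT. Section 4.6.2 adds nothing about baseline counts.

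**Baseline elsewhere.** Section 5.1.5 and Table 10 accept return to baseline as recovery. Table 10 footnote b says that if cytopenia comes mainly from lymphoma "infiltration of the bone marrow, the investigator may decide not to reduce the dose of lenalidomide". These provisions govern dosing, not DLT classification.

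**The concern.** The dosing rules recognize that a low count may reflect marrow disease rather than drug. The DLT definition, which selects the lenalidomide dose for about 40 expansion patients, does not. A patient stably at Grade 4 from entry, who takes all doses, occupies a full evaluable place and contributes a non-DLT on the affected duration criterion whatever the drug does to the marrow.

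This touches the toxicity most likely to separate the doses. Section 3.3.2.2 says that lenalidomide was set at 20 mg in the obinutuzumab–lenalidomide study because Grade 3 or 4 neutropenia increased at 25 mg. Section 5.1.4 names neutropenia as the main toxicity of that pair. With 3 to 6 patients per dosing group, the decision turns on one event against two.

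**Working it through.** **1. The plan's rule.** Section 3.1.2.2 accepts a dose when under 33% of evaluable patients have a DLT, expressed as at most one in six. Check: 1/6 = 16.7% passes and 2/6 = 33.3% fails, so the two statements agree. The 20 mg group goes to six unless two DLTs occur in the first three, so acceptance is exactly P(X ≤ 1) with X ~ Bin(6, p).

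**2. Which criteria fail at baseline Grade 4?**

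| Criterion in 3.1.2.1 | Patient already at Grade 4 from lymphoma |
|---|---|
| Grade 4 neutropenia or thrombocytopenia, more than 7 days | Uninformative for the affected cell line |
| Neutropenia with sustained fever or infection | Assessable |
| Thrombocytopenia with significant bleeding | Assessable |
| Delay of more than 14 days | Assessable |
| Non-hematologic Grade 3 or 4 | Assessable |

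**3. Which way would the affected criterion be scored?** A DLT needs investigator-assessed relatedness (3.1.2.1), and a pre-existing condition is an adverse event only if it worsens (5.3.6.9). Unchanged Grade 4 cytopenia from lymphoma meets neither condition, so the expected score is no DLT.

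**4. Size.** The assumptions, none of them given in the documents, are: true DLT rate p; independent patients; one affected patient among six; a share h of that patient's DLT probability unable to register. Then

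P(accept) = (1−p)^5 + 5p(1−p)^4 × [1 − p(1−h)].

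At p = 0.40, (1−p)^5 = 0.0778 and 5p(1−p)^4 = 0.2592:
- h = 0: 0.0778 + 0.2592 × 0.6 = 0.233
- h = 0.5: 0.0778 + 0.2592 × 0.8 = 0.285
- h = 1: 0.0778 + 0.2592 = 0.337

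At p = 0.20, the two terms are 0.3277 and 0.4096:
- h = 0: 0.3277 + 0.4096 × 0.8 = 0.655
- h = 0.5: 0.3277 + 0.4096 × 0.9 = 0.696
- h = 1: 0.3277 + 0.4096 = 0.737

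| True DLT rate | All six assessable | h = 0.5 | h = 1 (upper bound) |
|---|---|---|---|
| 20% | 65.5% | 69.6% | 73.7% |
| 25% | 53.4% | 58.3% | 63.3% |
| 33% | 35.8% | 41.3% | 46.8% |
| 40% | 23.3% | 28.5% | 33.7% |

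The h = 1 column removes every DLT for that patient, so it is a ceiling. The h = 0.5 column corresponds to half of DLTs being hematologic and all of those being masked. Losing only a duration criterion would give less.

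**The case against.** The strongest counter-argument is that the plan already filters on baseline, through relatedness and the worsening rule, and that other safeguards surround the decision. The sponsor approves each enrollment (4.2). Laboratory and adverse event data are reviewed before escalation decisions, and toxicity beyond Cycle 2 may be considered (3.1.2.2). The IMC reviews the data supporting the RP2D (3.1.4). If counts worsen and Table 10 leads to lenalidomide being withheld, an event judged unrelated that costs five consecutive doses triggers replacement anyway. The exclusion for contraindication to thromboembolism prophylaxis may act as a practical platelet floor. The DLT window is Cycle 2, so the count entering it need not equal the screening value. The documents give no frequency for such patients.

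Much of this stands, and it rules out two stronger readings that a reader might infer.

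- *That such a patient brings in a DLT already present at entry.* An automatic DLT would cut acceptance to (1−p)^5, which is 32.8% at p = 0.20 and 7.8% at p = 0.40. Relatedness and the worsening rule largely exclude this.
- *That the hematologic criteria as a whole cannot be assessed.* A patient below the entry limits but short of Grade 4 can still worsen to Grade 4 for more than 7 days. Even at baseline Grade 4, the criteria with a clinical component still work.

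What the safeguards do not repair is the denominator. Relatedness and worsening are left to unguided judgment, and at Grade 4 worsening cannot appear as a higher non-fatal grade. Attribution prevents a false DLT, but the patient stays in the count as a clean non-DLT. Neither the sponsor's review nor the practical platelet limit supplies a written rule, and the platelet point has no bearing on ANC.

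**Conclusion.** The point holds for a narrow group: escalation patients stably at Grade 4 neutropenia or thrombocytopenia from lymphoma since entry who receive their doses. For them the matching duration criterion is uninformative, yet Section 3.1.2 counts them as evaluable. The bias is toward accepting the dose. With one such patient among six, the increase is at most 10.4 percentage points at a true DLT rate of 40% (33.7 − 23.3), or about 5.2 points if half of DLTs are hematologic and all are masked (28.5 − 23.3). At 20% it is at most 8.2 points (73.7 − 65.5). These figures assume independence and that such a patient enrolls; the documents support no estimate of how often that would happen. It is a gap in a stated rule that feeds the RP2D decision. It does not show that dose selection is unsound overall.

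**What to change.** Reconcile Sections 3.1.2, 3.1.2.1 and 4.1.2 with the baseline language in Section 5.1.5 and Table 10 by adding one evaluability sentence to Section 3.1.2, along these lines:

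*A dose-escalation patient whose lymphoma-related baseline cytopenia already meets the grade used in a duration-based hematologic DLT criterion is not evaluable for that criterion. Any DLT that does occur counts. In the absence of a DLT, the patient is replaced for dose-escalation decisions.*

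The sponsor should set the exact baseline threshold and the time at which it is measured. The trigger should be the baseline grade, not the entry limits. If every patient below the entry limits were declared non-evaluable for the hematologic criteria, a genuine drug-related Grade 4 event in someone who entered only slightly below the ANC limit would be discarded.

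The cost is an occasional replaced escalation patient. Such a patient then enters the count only with a DLT, which leans toward caution. The plan's present rule for early discontinuation and missed doses already works this way.

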3.1.2.2 Treatment Regimens and Dose-Escalation Rules

A 3+3 dose-escalation schema will be used. Induction treatment will be administered in 28-day cycles, as outlined in Table 1. Obinutuzumab and atezolizumab will remain at fixed doses during the dose-escalation phase. For induction treatment, the starting dose for lenalidomide is 15 mg, which is one dose level below 20 mg, the RP2D identified for lenalidomide when given in combination with obinutuzumab in a Phase Ib/II study

(MO28005 [GALEN]). If the 15-mg dose is safe and tolerable, the lenalidomide dose will be escalated to 20 mg. Inpatient dose escalation is not allowed.

Table 1 Induction Treatment for Dose-Escalation Phase

Cycle(s)	Atezo+ G +Len (28-Day Cycles)
1	
 • Lenalidomide 15 or 20 mg^a PO once daily on Days 1–21 • Obinutuzumab 1000 mg IV on Days 1, 8, and 15
2–6	
 • Lenalidomide 15 or 20 mg^a PO once daily on Days 1–21 • Obinutuzumab 1000 mg IV on Day 1 • Atezolizumab 840 mg IV on Days 1 and 15

IV=intravenous; PO=by mouth.

^a Dose may be de-escalated to 10 mg.

Dose escalation will occur in accordance with the rules listed below.

First Dosing Group (15 mg of Lenalidomide)

- A minimum of 3 patients will initially be enrolled in the first dosing group (15 mg of lenalidomide). Patients within the dosing group may be treated in parallel.
- If none of the first 3 DLT-evaluable patients experiences a DLT, enrollment of the second dosing group (i.e., 20 mg of lenalidomide) may proceed.
- If 1 of the first 3 DLT-evaluable patients experiences a DLT, the dosing group will be expanded to at least 6 patients. If there are no further DLTs in the first 6 DLT-evaluable patients, enrollment of the second dosing group may proceed.
- If 2 or more of the first 3 DLT-evaluable patients experience a DLT, the RP2D will have been exceeded, and dose escalation will stop. The Medical Monitor, in discussion with the Principal Investigator and participant investigators, may decide to proceed with dose de-escalation and enroll patients at 10 mg of lenalidomide, following the same 3+3 design.
- If 2 or more of the first 6 DLT-evaluable patients experience a DLT, the RP2D will have been exceeded, and dose escalation will stop. The Medical Monitor, in discussion with the Principal Investigator and participant investigators, may decide to proceed with dose de-escalation and enroll patients at 10 mg of lenalidomide, following the same 3+3 design.

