4.3.2.3 Lenalidomide

Lenalidomide will be administered orally once daily on Days 1–21 of Cycles 1–6 (28-day cycles) during induction treatment and on Days 1–21 of each month during maintenance treatment. During the dose-escalation phase, lenalidomide will be administered at a dose of 15 or 20 mg (dose may be de-escalated to 10 mg) during induction treatment and at 10 mg during maintenance treatment. During the expansion phase, lenalidomide will be administered at the RP2D during induction treatment and at 10 mg during maintenance treatment.

Lenalidomide capsules should be swallowed whole with water and should not be broken, chewed, or opened. The capsules may be taken with or without food, except on lenalidomide PK sampling days (see [Appendix 2](#)), when the patient should fast (water allowed) at least 2 hours before and at least 1 hour after the lenalidomide dose. On lenalidomide PK sampling visits, lenalidomide dose will be taken in the clinic.

Lenalidomide should be administered at approximately the same time each day. If a dose of lenalidomide is missed and it has been < 12 hours since the time of the scheduled dose, the patient may take the missed dose. If it has been > 12 hours, the dose should be skipped and the next dose should be taken at the regularly scheduled time. Two doses should not be taken at the same time. If a dose had been vomited, the dose should not be re-taken.

At each cycle, each patient will be supplied with only enough lenalidomide for that cycle. A drug diary will be provided to the patient to record oral administration of doses, including the date and time. Patients will be instructed to return empty bottles or unused capsules. The investigator is responsible for monitoring patient compliance by monitoring the patient diary and counting unused capsules.

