5.1.3.8 Renal Impairment

Lenalidomide is substantially excreted by the kidney. Patients with renal impairment (i.e., calculated creatinine clearance < 60 mL/min) will not be enrolled in this study. Renal function will be monitored during the study, and the lenalidomide dose may be adjusted as outlined in Section [5.1.5](#) (see [Table 10](#)).

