5.1.5 Management of Specific Adverse Events

Study treatment may be delayed for toxicity for a maximum amount of time, as specified in the tables below. If study treatment is delayed for longer than the specified maximum, study treatment will be permanently discontinued. Treatment delays apply to all toxicities described below; dose modifications apply only to toxicities that are considered

to be related to lenalidomide. There will be no dose reductions of obinutuzumab or atezolizumab.

The lenalidomide dose may be reduced in 5-mg increments one or two times, depending on the starting dose, as outlined in [Table 9](#). There will be no more than one dose reduction per treatment cycle. If the lenalidomide dose is reduced, re-escalation is not permitted.

Table 9 Lenalidomide Dose Reduction

Starting Dose	First Reduction	Second Reduction
20 mg	15 mg	10 mg
15 mg	10 mg	5 mg
10 mg	5 mg	—

If a lenalidomide-related toxicity occurs during lenalidomide treatment (i.e., before Day 21 of the cycle), lenalidomide must be withheld until criteria for recovery have been met (i.e., improves to Grade ≤ 2 or baseline values).

If recovery is observed prior or on Day 15 of the cycle, lenalidomide may be resumed at the same dose for the remainder of the cycle (through Day 21; missed doses will not be made up) at the discretion of the investigator. If the investigator considers that resuming lenalidomide at the same dose within the cycle represents an unacceptable risk for the patient, lenalidomide shall be resumed at reduced dose or withheld for the remainder of the cycle. For subsequent cycles, lenalidomide will be resumed at reduced doses.

If recovery is observed after Day 15 of the cycle, lenalidomide will not be resumed for the current cycle. For subsequent cycles, lenalidomide will be resumed at reduced doses.

Guidelines for management of toxicities during induction are provided in [Section 5.1.5.1](#). Guidelines for management of toxicities during maintenance are provided in [Section 5.1.5.2](#).

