IRRs and anaphylaxis	
 • Guidelines for management of IRRs are provided in Sections 4.3.2.1 (obinutuzumab) and 4.3.2.2 (atezolizumab). • Metamizole (dipyrone) is prohibited in treating atezolizumab-associated IRRs because of its potential for causing agranulocytosis. • In case of anaphylaxis, study treatment should be permanently discontinued.
Renal toxicity	
 • Adjust the dose of lenalidomide^a as outlined below: 
 – If creatinine clearance is ≥ 30 but < 60 mL/min, lenalidomide should be given at a dose of 10 mg/day. – If creatinine clearance is < 30 mL/min and dialysis is not required, lenalidomide should be given at a dose of 10 mg every other day. – If creatinine clearance is < 30 mL/min and dialysis is required, lenalidomide should be given at a dose of 5 mg/day. On dialysis days, the dose should be administered after dialysis.

Table 11 Guidelines for Management of Non-Hematologic Toxicities (cont.)

	Event	Action to Be Taken
TLS	Clinical TLS ^b	
 • Withhold study treatment. • Correct electrolyte abnormalities, monitor renal function and fluid balance, and administer supportive care, including dialysis as indicated. Rasburicase therapy (if approved by the local health authority) may be administered as needed to reduce hyperuricemia. • If symptoms resolve completely, resume atezolizumab and obinutuzumab at full dose and resume lenalidomide at a reduced dose^a per guidelines in Section 5.1.5 for current and subsequent cycles. • Perform chemistry panel every other day for the first week after re-initiation of lenalidomide.
	Laboratory TLS ^b	
 • Withhold study treatment. • Correct electrolyte abnormalities, monitor renal function and fluid balance, and administer supportive care as clinically indicated. • If laboratory abnormalities have resolved completely, resume atezolizumab and obinutuzumab at full dose and resume lenalidomide either at current dose or at a reduced dose^a per guidelines in Section 5.1.5 for current and subsequent cycle, at the investigator's discretion.
Peripheral neuropathy	Grade 4 or Myasthenia gravis (any grade) or Guillain-Barre (any grade)	
 • Permanently discontinue study treatment. • Initiate treatment as per institutional guidelines.

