	Grade 2	
 Withhold study treatment. If there is improvement to Grade ≤ 1 or baseline, resume obinutuzumab and atezolizumab at full dose and resume lenalidomide at current dose. For Grade 2 laboratory abnormalities that are isolated, asymptomatic and considered not clinically significant treatment may be continued at the current dose at the investigator's discretion.

CT= computed tomography; FL= follicular lymphoma; G-CSF=granulocyte colony-stimulating factor; HLH =hemophagocytic lymphohistiocytosis; IRR=infusion-related reaction; IV=intravenous; LMWH=low-molecular-weight heparin; MAS =macrophage activation syndrome; NCI CTCAE=National Cancer Institute Common Terminology Criteria for Adverse Events; NHL =non-Hodgkin's lymphoma; NSAID =nonsteroidal anti-inflammatory drug; TLS=tumor lysis syndrome; TSH=thyroid-stimulating hormone; ULN=upper limit normal.

^a Dose modifications apply only to events that are considered to be related to lenalidomide.

^b According to Cairo-Bishop classification system.

^c Graded according to NCI CTCAE Version 3.0.

^d Atezolizumab may be withheld for a longer period of time (i.e., > 12 weeks after event onset) to allow for corticosteroids (if initiated) to be reduced to the equivalent of ≤ 10 mg/day oral prednisone. The acceptable length of the extended period of time must be agreed upon by the investigator and the Medical Monitor.

^e If corticosteroids have been initiated, they must be tapered over ≥ 1 month to the equivalent of ≤ 10 mg/day oral prednisone before atezolizumab can be resumed.

^f Resumption of atezolizumab may be considered in patients who are deriving benefit and have fully recovered from the immune-mediated event. Patients can be re-challenged with atezolizumab only after approval has been documented by both the investigator (or an appropriate delegate) and the Medical Monitor.

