- ^l Includes hemoglobin, hematocrit, platelet count, RBC count, WBC count, and percent or absolute WBC differential count (neutrophils, eosinophils, basophils, monocytes, lymphocytes, other cells).
- ^m Screening laboratory assessments may be used for Day 1 of Cycle 1 if performed within 72 hours prior to Day 1 of Cycle 1.
- ⁿ Perform hematology and chemistry tests within 72 hours prior to Day 1 of each cycle during induction or each month during maintenance, and within 24 hours prior to other timepoints during induction treatment. Samples for exploratory biomarker research should be collected at the same time as hematology and chemistry samples.
- ^o Cycles 2 and 3 only.
- ^p Includes sodium, potassium, glucose, BUN or urea, creatinine, calculated creatinine clearance, calcium, total bilirubin, direct bilirubin, total protein, albumin, ALT, AST, alkaline phosphatase, amylase, lipase, LDH, and uric acid.

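### Creatinine clearance below 60 mL/min is exempted when due to lymphoma in Section 4.1.2 but barred outright in Section 5.1.3.8, and an exempted patient's lenalidomide starting dose is unclear

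*Combined protocol and SAP*

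**What the plan says.** **Eligibility.** Section 4.1.2 introduces a group of laboratory exclusions with "Any of the following abnormal laboratory values (unless due to underlying lymphoma". Calculated creatinine clearance below 60 mL/min (Cockcroft-Gault) heads the list. The synopsis has the same introduction and the same item. Neither sets a lower limit on the clearance that the exemption can admit.

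**Safety plan.** Section 5.1.3.8 notes that lenalidomide is eliminated largely by the kidney and says that patients with renal impairment, defined as "calculated creatinine clearance < 60 mL/min) will not be enrolled in this study". It mentions no exemption. Appendix 10 likewise says that eligible patients must have adequate renal function.

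**Starting dose.** In Section 3.1.2.2, "the starting dose for lenalidomide is 15 mg" for the first dosing group. Section 4.3.2.3 says that in dose escalation "lenalidomide will be administered at a dose of 15 or 20 mg", with possible de-escalation to 10 mg, and that expansion patients receive the RP2D. None of these doses depends on baseline renal function.

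**Renal dosing.** The renal toxicity row of Table 11 (Section 5.1.5.1) is the only place where the lenalidomide dose depends on clearance. At 30 to below 60 mL/min, "lenalidomide should be given at a dose of 10 mg/day". Below 30 mL/min it is 10 mg every other day without dialysis, and 5 mg/day with dialysis. The row carries footnote a: "Dose modifications apply only to events that are considered to be related to lenalidomide". Section 5.1.5 says the same of all the toxicity tables: "dose modifications apply only to toxicities that are considered" to be lenalidomide-related.

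**The concern.** The same threshold leads to two different enrollment decisions. A reader of Section 4.1.2 may put forward a patient who, according to Section 5.1.3.8, is not in the study. The safety plan then describes a protection that the operative criteria do not provide.

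The exemption also fits poorly with the reason for the limit. Reduced elimination of a renally cleared drug matters whether lymphoma or something else lowered the clearance.

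The dosing text is least clear for exactly the patient the exemption admits. Before the first dose, that patient's renal impairment cannot be related to lenalidomide. Read literally, footnote a takes the patient outside the renal row. What is at stake is the safety of a small number of patients, and one consistent answer for sites on who may enter and at what dose.

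**Working it through.** No figure in the plan needs reproducing. The check sets the texts side by side and takes one ratio.

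**Step 1: may the patient enter?** Take a patient with clearance of 30 to below 60 mL/min due to lymphoma.

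- Section 4.1.2 and the synopsis: not excluded.
- Section 5.1.3.8: not enrolled.

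The two answers conflict.

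**Step 2: what is the starting dose?**

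- Sections 3.1.2.2 and 4.3.2.3: 15 mg, 20 mg or the RP2D (10 mg only after de-escalation).
- Table 11 renal row, if it applies at baseline: 10 mg/day.
- Does it apply? The row is worded by clearance value, and Appendix 1 says "Perform hematology and chemistry tests within 72 hours prior to Day 1 of each cycle during induction". A site therefore has the value in time to use the row on Cycle 1 Day 1. Against that, the row is headed as a toxicity, and footnote a and Section 5.1.5 limit modifications to lenalidomide-related events. The text supports either reading.

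**Step 3: size of the difference at 30 to below 60 mL/min.** Ratio = starting dose / Table 11 dose.

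| Starting dose | Row does not apply at baseline | Row applies at baseline |
|---|---|---|
| 15 mg | 15 / 10 = 1.5 | 10 / 10 = 1 |
| 20 mg | 20 / 10 = 2 | 10 / 10 = 1 |
| 10 mg (RP2D after de-escalation) | 10 / 10 = 1 | 10 / 10 = 1 |

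Maintenance is 10 mg for every patient, which equals the Table 11 dose in this band, so no excess arises there.

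**Step 4: the cross-reference.** Section 5.1.3.8 sends the reader to Table 10 for renal adjustment. Table 10 covers hematologic toxicity only; the renal row is in Table 11.

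**The case against.** Section 4.1 is where eligibility is set, and Section 5.1.3.8 belongs to a risk summary. It can be read as shorthand that leaves out the exemption. Even on that reading the wording still conflicts, and the safety plan claims more than the criteria deliver.

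A reader might infer that a site could enroll such a patient on its own. It could not: Section 4.2 requires the sponsor to review the eligibility documents and approve each enrollment. That may catch a case, but the sponsor's reviewer works from the same conflicting text. The ban on eligibility waivers in Section 9.2 does not help, because a patient who meets the exemption needs no waiver.

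A reader might also infer that the protocol has no renal dosing for these patients. Table 11 in fact gives a dose for every clearance below 60 mL/min, including on dialysis. There is a good argument that its purpose is to match the dose to elimination. Limiting it to lenalidomide-caused impairment would withhold the reduced dose from anyone whose kidneys failed for another reason. That argument has force, and a careful site would probably act on it. It does not remove footnote a, which is attached to the row.

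Finally, a reader might carry the excess over all six induction cycles. The documents do not support such a total. It would need clearance to go uncorrected although chemistry, including calculated clearance, is scheduled on Days 1, 8, 15 and 22 of Cycles 1 to 3 and on Days 1 and 15 of Cycles 4 to 6. It would also need no reduction for toxicity under Section 5.1.5. The supportable measure is the starting-dose ratio.

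**Conclusion.** The contradiction on enrollment is plain on the text. The dosing consequence is conditional. If the Table 11 renal row does not reach lymphoma-caused impairment at baseline, a patient at 30 to below 60 mL/min starts at 1.5 times (15 mg) or 2 times (20 mg) the dose that the protocol uses for that clearance. If the row does apply, or the RP2D is 10 mg, there is no excess in that band.

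It would go too far to say that the plan overdoses these patients: the text leaves the dose unclear and does not prescribe the higher one. The documents do not say how often the exemption would be used; it is assumed to be rare. The primary endpoint and sample size are unaffected. The point deserves correction because it concerns eligibility and dosing of a renally cleared drug and is easily settled.

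**What to change.** **Preferred.** In Section 4.1.2 and the synopsis, move creatinine clearance below 60 mL/min out from under the lymphoma exemption, so that it is an absolute exclusion matching Section 5.1.3.8. The cost is one item moved in two places; the downside is that a few patients with lymphoma-related renal impairment become ineligible.

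**If the sponsor wants to keep the exemption.** State it in Section 5.1.3.8, and add a sentence that the Table 11 clearance bands set the lenalidomide dose from Cycle 1 Day 1 regardless of the cause of the impairment. This keeps those patients eligible and costs two short text changes.

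**In either case.** Change the Table 10 reference in Section 5.1.3.8 to Table 11. The same slip in Sections 5.1.3.4, 5.1.3.5 and 5.1.3.7 is editorial only and has no bearing on renal eligibility.
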